17.5.15.2. Analysis

The analysis will use the method of the two sample t test or Mann Whitney U test depending

on the distribution of the data. Means will be presented with 95% confidence intervals or

medians and interquartile range as appropriate.

The proportion of days in the primary outcome time window spent on parenteral nutrition will

be reported.

17.5.16. Death

17.5.16.1. Within 6 months (26 weeks) of randomisation

17.5.16.1.1 Derivation

If a baby has died within 26 weeks of randomisation and before discharge, see section

17.5.16.2.1 for details on where this information is captured. For the babies who are alive at

discharge home from neonatal care, PDS data will be used to determine the baby's status at

26 weeks.

17.5.16.1.2 Analysis

The analysis will use the method of Fisher's exact test to compare proportions in the standard

group compared to the impregnated group and relative risks will be presented with 95%

confidence intervals. This will be presented in two ways:

Using CRF data only

• Using CRF and PDS data combined once available.

17.5.16.2. Before discharge home from neonatal care

17.5.16.2.1 **Derivation**

This is a binary outcome with a "Yes/No" response. Whether a baby has died can be found on

CRF "Form 7a: Clinical Outcomes" under section 1. It should be noted that Form 7a is

completed each time a baby is transferred and so there may be more than one "Form 7a" for

each baby. If "Yes" is selected on any completed 'Form 7a' then the outcome is "Yes" for that

baby, if "No" is selected on all forms then the outcome is "No".

17.5.16.2.2 **Analysis**

The analysis will use the method of Fisher's exact test to compare proportions in the standard

group compared to the impregnated group and relative risks will be presented with 95%

confidence intervals.

17.5.16.3. Time to death

17.5.16.3.1 Derivation

If a baby has died within 26 weeks of randomisation and before discharge, see section

17.5.16.2.1 for details on where this information is captured. There will be an initial analysis

performed on this dataset. For the babies who are alive at discharge home from neonatal care,

PDS data will be used to determine the baby's status at 26 weeks and the initial analysis will

be updated to take into account this information.

17.5.16.3.2 **Analysis**

The survival analysis will use the method of the Log rank test and Cox proportional hazard

regression models if appropriate. Results will be presented using Hazard Ratios and 95%

confidence intervals. Kaplan-Meier curves stratified by treatment will be presented. Survival

times will be measured from the date of randomisation to the date of death. This will be

presented in two ways:

Using CRF data only

• Using CRF and PDS data combined once available.

18. Missing data and withdrawals

The numbers (with reasons) of losses to follow-up and withdrawals over the course of the trial

will be summarised by treatment arm. This will be presented in a CONSORT diagram

alongside a table detailing numbers and reasons for withdrawal and/or exclusion from

analysis.

The primary outcome is time to event so even if babies are withdrawn or lost to follow up, they

will still contribute to the primary analysis up to the point of withdrawal or lost to follow up

provided that parents do not remove consent to use data that has been collected up to that

point. Where dates are known but times are missing, times will be imputed as 12:00. The

number of babies where imputation is used will be reported.

19. Additional analyses

19.1 Sensitivity analyses: Primary outcome

Four sensitivity analyses will be undertaken on the primary outcome.

19.1.1. Time to first clinically serious BSI

Time to first clinically serious BSI where clinically serious BSI is defined by a BSI as defined

in section 17.4.1.1 and the baby is treated for more than 72 hours or more of antimicrobials

(found on Form 5: Microbiology) or dies during treatment (determined from date and time of

death captured on Form 7a: Clinical Outcomes). The analysis will be the same as in section

17.4.1.2.

Note: it was identified during blind review that the definition of this sensitivity analysis in the

protocol and previous versions of this SAP did not capture all cases of clinically serious BSI

as antibiotics are only used to treat bacterial infections, whereas BSI includes bacterial and

fungal infections.

19.1.2. Time to first BSI from insertion

Time to first BSI where BSI is defined as in section 17.4.1.1 but survival times will be calculated

from date and time of insertion rather than date and time of randomisation. The analysis will

be the same as in section 17.4.1.2. Babies with no line inserted will be excluded.

19.1.3. Time to first BSI excluding arterial or CVC samples

Time to first BSI where BSI is defined as in section 17.4.1.1 but excluding arterial or CVC

samples. The analysis will be the same as in section 17.4.1.2.

19.1.4. Time to first BSI only including "clearly pathogenic organisms"

Time to first BSI where BSI is defined as in section 17.4.1.1 but only including "clearly

pathogenic organisms" (as defined in Section 23.2 Appendix II) as positive cultures.

19.2 Sensitivity analyses: Secondary outcomes

Sensitivity analyses will be undertaken to complement some of the secondary outcomes to

test the robustness of the results drawn from the main analyses.

19.2.1. Rate of BSI per 1000 PICC-days over total time that the line is in situ

Rate of BSI per 1000 PICC-days (including recurrent BSI) using the total number of

independent episodes of BSI that occur when the line is in situ and the total number of days

that the line is in situ. The analysis will be the same as in section 17.5.4.2. A table will be

presented showing the timings of BSIs.

19.2.2. Rate of catheter-related BSI per 1000 PICC-days over total time that the

line is in situ

Rate of catheter-related BSI per 1000 PICC using the total number of independent episodes

of catheter related BSI that occur when the line is in situ and the total number of days that the

line is in situ. The analysis will be the same as in section 17.5.6.2.

19.2.3. Rate of blood/CSF culture sampling per 1000 PICC-days over total time

that the line is in situ

Rate of blood/CSF culture sampling per 1000 PICC days using the total number of blood/CSF

samples taken when the line is in situ and the total number of days that the line is in situ. The

analysis will be the same as in section 17.5.7.2.

19.2.4. Type of organism grown (clinically serious BSI)

The definition of clinically serious BSI can be found in section 19.1.1. The analysis will be the

same as in section 17.5.3.2.

19.2.5. Type of organism grown (from BSI excluding arterial or CVC samples)

The definition of BSI excluding arterial or CVC samples can be found in section 19.1.3. The

analysis will be the same as in section 17.5.3.2.

19.2.6. Type of organism grown (from BSI only including "clearly pathogenic

organisms")

The definition of BSI only including "clearly pathogenic organisms" can be found in section

19.1.4. The analysis will be the same as in section 17.5.3.2.

19.3 Additional secondary analyses

In addition to the secondary outcomes for Rifampicin resistance listed in sections 17.5.1 and

17.5.2, Rifampicin resistance in any isolate from blood/CSF cultures or PICC tips will be

presented. This outcome is not pre-specified within the protocol but has been requested by

the chief investigators prior to them seeing any unblinded data.

This is a binary outcome of 'Yes/No' for each baby. Rifampicin resistance can be found on

CRF "Form 5: Microbiology". For rifampicin resistance to be tested, "organism cultured" must

be anything except zero, and the E-test must be selected as being performed. If the Rifampicin

minimum inhibitory concentration value is >0.5 mg/L then the sample is classed as being

resistant to rifampicin. If a baby has any blood/CSF or PICC tip sample which is rifampicin

resistant, then this will be classed as "yes" for that baby.

The analysis will use the method of Fisher's exact test to compare proportions of babies with

rifampicin resistant samples in the standard group compared to the impregnated group and

relative risks will be presented with 95% confidence intervals.

20. Safety Evaluations

20.1. Data sets analysed

Adverse events will be summarised descriptively with babies analysed according to the

treatment they received.

All babies who either had a PICC inserted or had an attempted insertion will be included within

the safety analysis population. Babies that had a PICC inserted will be analysed according to

the treatment they received. If a baby had an attempted insertion but did not have a PICC

successfully inserted then as it is not captured which PICC was attempted, the baby will be

analysed according to the treatment group they were randomised to.

20.2. Presentation of the data

Adverse events (AEs) and serious adverse events (SAEs) reported by the clinical investigator

and are classified as "possibly", "probably" or "almost certainly" related to the study treatment

will be presented by treatment group. The number (and percentage) of babies experiencing

each AE/SAE will be presented for each treatment arm categorised by severity. For each baby, only the maximum severity experienced of each type of AE will be displayed. The number (and percentage) of occurrences of each AE/SAE will also be presented for each treatment arm. No formal statistical testing will be undertaken.

Adverse events will be categorised according to severity as "Mild", "Moderate", or "Severe". They will also be classified in relation to the causality with the treatment as "Possibly", "Probably", or "Almost certainly". Full details on the definition and classification of these adverse events are presented in section 10 of the protocol.

21. Quality Control

To ensure quality control, an independent statistician will follow this SAP to independently program the primary analysis from the raw data. Any discrepancies found will be discussed with the trial statistician to resolve. No programming will be shared or shown between the statisticians. The independent statistician will also check the report against their output obtained from the statistical software.

[figure not shown]
22. References

- 1. International Conference on Harmonisation. Topic E9 Statistical Principles for Clinical Trials (CPMP/ICH/363/96). 1998.
- 2. Guidance on Statistical Analysis Plans.
- 4. Shuster JJ: Diagnostics for assumptions in moderate to large simple clinical trials: do they really help? Stat Med 2005, 24(16):2431–2438.
- 7. UK Standard for Microbiology Investigations: Introduction to the Preliminary Identification of Medically Important Bacteria. Bacteriology Identification, ID 1, Issue no: 1.6, Issue date: 12.03.2014, p14-17

Page 36 of 38

23. Appendices

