8.4.3. Removal of patients from therapy or assessment

All babies will have their PICC removed at some point. Case report form (CRF) "Form 6:

Removal" records the reason for PICC removal. These include:

PICC no longer needed

Removed because of confirmed infection

Removed because of suspected infection

Damaged

Unintended removal

PICC blocked

Thrombosis

Clinically evident thrombophlebitis

Pre-specified duration of use reached

Malposition identified during x-ray

Babies will be observed for clinical follow-up for 48 hours after the PICC removal and a

retrospective review of key events will take place when the baby is discharged

home/dies/reached 26 weeks post randomisation, unless the parent/legal representative

instructs otherwise.

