8.6. Blinding

This is an open-label trial because AM-PICCs can be distinguished from S-PICCs as rifampicin

causes brown staining on the tubing. No details on blinding will be presented.

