8.8. Sequence and duration of all study periods

A schematic of the study design can be found in section 1 of the study protocol. A table of trial

assessments can be found in section 8.1 of the protocol.

To summarise this information, the researcher (clinician or research nurse) will approach

parents of eligible babies to discuss PREVAIL and to obtain consent. Once consent is

obtained, the baby will then be randomised to either AM-PICC or S-PICC. Consent is valid for

14 days. If the baby has not been randomised within 14 days, the parents will need to

reconsent. Babies are followed up clinically and for safety until 48 hours after removal or

attempted insertion (if attempted but not inserted) or randomisation (if randomised but not

inserted). There is a retrospective review of key events at discharge home from neonatal care,

death or 26 weeks post randomisation, whichever occurs first and at all transfers to other

hospitals.

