17.3. Presentation of data for treatment adherence

Tables mentioned within this section will be presented overall and split by treatment.

Frequency tables (with percentages) will be presented for:

Reasons for PICC removal

• The number of babies whose PICC was removed less than 24 hours after

randomisation

The number of babies receiving the allocated PICC

The number of babies receiving a non-allocated PICC

The number of babies randomised but did not receive any PICC

The type of sample and whether an e-test was performed for positive cultures

• Length of time PICC is in situ for (from insertion to removal).

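### The AE/SAE tables by arm show only events classed as related to treatment in an open-label trial, so for event types not compared elsewhere they mix occurrence with unblinded attribution (minor)

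*SAP*

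**What the plan says.** Section 20.2 presents by treatment group the AEs and SAEs that the clinical investigator reports and that "are classified as 'possibly', 'probably' or 'almost certainly' related to the study treatment". Babies and occurrences are counted, babies are categorised by severity, and nothing is tested. On grading, the section says: "They will also be classified in relation to the causality with the treatment as 'Possibly', 'Probably', or 'Almost certainly". It names no grade below these three and refers the rest elsewhere: "Full details on the definition and classification of these adverse events are presented in section 10 of the protocol". No other AE or SAE table appears in the SAP.

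On blinding, section 8.6 says: "This is an open-label trial because AM-PICCs can be distinguished from S-PICCs as rifampicin" stains the tubing brown. Section 17.4.1.1 has the clinical team's microbiology decisions for the primary outcome made without knowledge of the arm. Nothing equivalent is stated for AE causality.

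On the period covered, section 8.8 reads: "Babies are followed up clinically and for safety until 48 hours after removal or" and continues "attempted insertion (if attempted but not inserted) or randomisation (if randomised but not" inserted). Section 20.1 puts every baby with an inserted PICC or an attempted insertion in the safety population.

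Section 17.3 also tabulates "Reasons for PICC removal" overall and by treatment. The reasons listed in 8.4.3 include thrombosis and "Clinically evident thrombophlebitis".

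**The concern.** Whether an event is related to the line is a judgement. Here the arms can be told apart by sight, and the SAP does not say that this judgement is made blind. If staff attribute events to an impregnated line more or less readily than to a standard one, a table restricted to related events will show a difference between arms, or hide one, for reasons other than how often the events happened. A reader of the table cannot separate the two components.

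Section 6 of the SAP names the safety of the impregnated line among the things on which neonatologists need clear evidence. What is at stake is how the AE table can be read for events that the SAP compares nowhere else. No hypothesis test depends on it.

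**Working it through.** The SAP states no AE rate and no attribution rate, so there is no figure to reproduce. The check has two parts: which harms escape the filter, and what the filter could do to the rest.

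**1. What is compared by arm without a causality grade**

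- Bloodstream infection: time to first BSI (17.4.1), BSI rate (17.5.4), occurrence of one or more BSI (17.5.5) and catheter-related BSI (17.5.6). The primary outcome window runs to 48 hours after PICC removal.
- Rifampicin resistance: blood/CSF, PICC tips, or either (17.5.1, 17.5.2, 19.3), 3 comparisons.
- Chronic lung disease, NEC, retinopathy treatment and cranial ultrasound abnormality (17.5.10 to 17.5.13), 4 comparisons.
- Death: within 26 weeks, before discharge home, and time to death (17.5.16), 3 comparisons.
- Removal reasons (17.3). Section 8.4.3 lists 10: 6 line problems (damaged, unintended removal, blocked, thrombosis, thrombophlebitis, malposition) + 2 for infection (confirmed, suspected) + 2 planned (no longer needed, pre-specified duration reached).

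Leaving BSI and removal reasons aside, that is 3 + 4 + 3 = 10 comparisons free of attribution.

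**2. What is left**

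A removal reason exists only when a line was in place and was taken out, and it records why. Three kinds of event can fall outside both the outcomes above and the removal reasons:

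- a line complication managed without removing the line;
- a complication arising in the 48 hours after removal, still within safety follow-up (8.8);
- a complication after a failed insertion. These babies are in the safety population (20.1) but have no removal reason.

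Unless such an event is also one of the outcomes in part 1, it reaches a table by arm only if it is classed as related.

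**3. What the filter can do to these events (illustration on assumed values)**

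Displayed ratio (AM-PICC / S-PICC) = true ratio × (attribution probability in AM-PICC / attribution probability in S-PICC).

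A true ratio R shows as 1.00 when the attribution ratio is 1/R:

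| True ratio | Attribution ratio that hides it |
|---|---|
| 1.25 | 1/1.25 = 0.80 |
| 1.5 | 1/1.5 = 0.67 |
| 2.0 | 1/2.0 = 0.50 |

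With no true difference and attribution assumed to lie anywhere from 30% to 50% in each arm, the displayed ratio runs from 0.30/0.50 = 0.60 to 0.50/0.30 = 1.67. It is 1.00 if attribution is equal. None of these inputs comes from the SAP. They show that the distortion can go either way, and they do not estimate its size.

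**The case against.** The strongest objection is that 20.2 may simply tabulate whatever investigators are required to report. It lists only three related grades and leaves definitions to protocol section 10. If only related events are recorded, the restriction is a data-collection rule set elsewhere and an additional table would add no rows. That possibility stands, and the SAP alone cannot settle it. It does not remove the point: in either case the displayed comparison depends on an unblinded judgement, and 20.2 does not say so.

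It can also be said that the table is descriptive, that its filter is declared in advance, that possibly is an inclusive threshold, and that the main harms of prematurity are already outcomes. All of this is right, and it is why the point is minor. The absence of a test does not take the filter out of the counts and percentages that readers will compare.

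Three stronger readings are tempting, and the documents do not support them.

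- A reader might infer that safety follow-up reaches further than the attribution-free comparisons, so that any event after removal or a failed insertion is seen only if classed as related. For the outcomes captured to discharge home, death or 6 months (9.2), safety follow-up is shorter. The safety population is also narrower than all randomised babies (17.1, 20.1). Death, NEC, chronic lung disease, treated retinopathy or a cranial ultrasound abnormality after removal is compared with no causality filter, and so is a positive blood/CSF culture up to 48 hours after removal.
- A reader might infer that attribution does differ between arms. The SAP contains no evidence that it does.
- A reader might infer that unrelated events sit on the database and are being dropped. The SAP does not say whether they are recorded.

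**Conclusion.** The point holds in a narrow form and is minor. The only AE/SAE tables in the SAP admit events by relatedness, in a trial whose arms are visibly different and with no blinded causality assessment stated. For the residual event types, the comparison by arm cannot be read as a comparison of occurrence. Size and direction are unknown.

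The conclusion assumes that some reportable events fall in that residue, that relatedness is judged by people who can see the line, and that protocol section 10 contains no blinded causality review. The primary outcome, the secondary outcomes and the removal-reason table are unaffected.

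**What to change.** In 20.2, tabulate by treatment group all AEs and SAEs recorded on the database irrespective of causality, giving babies and occurrences and using severity as now, with the possibly, probably and almost certainly related events as a labelled subset. First check protocol section 10. If it has only related events recorded, state in 20.2 that the table depends on unblinded attribution and should be read accordingly.

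The cost is one sentence and, where unrelated events are recorded, one further set of descriptive tables. The downside is longer tables that include background events of prematurity. No outcome definition, model or test changes.

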23.1. Appendix I

23.2. Appendix II

Organisms coded on Form 5: Microbiology will be classified as follows:

Organism	Pathogen group		
Coagulase-negative staphylococcus	Potential pathogen or likely contaminant		
Staph aureus	Clearly pathogenic organism		
Klebsiella spp.	Clearly pathogenic organism		
Enterobacter spp.	Clearly pathogenic organism		
Pseudomonas aeruginosa	Clearly pathogenic organism		
Acinetobacter spp.	Clearly pathogenic organism		
E.coli	Clearly pathogenic organism		
Enterococcus spp.	Clearly pathogenic organism		
Candida Albicans	Clearly pathogenic organism		
Non candida albicans species	Clearly pathogenic organism		

Organisms coded as 'Other' will be referred to the clinical team for confirmation. Classifications will be made as follows but as the 'Other' organisms will be written in free text clinical interpretation is required.

Organism	Pathogen group			
Gram Positive				
Group B Streptococci	Clearly pathogenic organism			
Streptococcus (other)	Potential pathogen or likely contaminant			
Micrococcus sp.	Potential pathogen or likely contaminant			
Bacillus sp.	Clearly pathogenic organism			
Diphtheroids	Potential pathogen or likely contaminant			
Streptococcus pneumoniae	Clearly pathogenic organism			
Propionibacterium acnes	Potential pathogen or likely contaminant			
Listeria monocytogenes	Clearly pathogenic organism			
Other Gram Positive	Need to review name of isolated species			
Gram Negative				
Pseudomonas sp.	Clearly pathogenic organism			
Serratia sp.	Clearly pathogenic organism			
Coliform	Clearly pathogenic organism			
Citrobacter sp.	Clearly pathogenic organism			
Burkholderia sp.	Clearly pathogenic organism			
Haemophilus sp.	Clearly pathogenic organism			
Other Gram negative	Need to review name of isolated species			
Fungi				
Candida (other)	Clearly pathogenic organism			
Other Fungi	Clearly pathogenic organism			
Other fungal organism	Clearly pathogenic organism
